6.2.2 Entry Evaluations

Entry evaluations, including collection of all entry specimens, must occur at least 48 hours after screening evaluations, unless otherwise specified, and prior to the **participant's** starting any study medications, treatments, or interventions.

6.2.3 Post-Entry Evaluations

Prior to starting sirolimus, laboratory measurements from the week 12 visit must be assessed to ensure that the criteria detailed in section 4.1.6 and 4.1.10 continue to be satisfied, as well as week 12 CD4+ cell count >300 cells/mm³. If any criterion is not satisfied, the study team should be promptly contacted and sirolimus should not be started. In addition, concomitant medications must be re-assessed at the week 12 visit to ensure that the **participant** has not received any prohibited medications since study entry. If so, the study team should be promptly contacted and sirolimus should not be started.

Participants must begin study treatment within 72 hours after receipt of results from the study week 12 evaluations.

Site staff is encouraged to contact **participants** at least 14 days prior to scheduled study visits (not PK-only visits) to remind **participants** not to receive any vaccinations prior to their visit. A reminder can also be given that prohibited medications are not allowed at any time while on study.

For stored samples, all sites must have established procedures for regular reconciliation and verification of specimens, which must be followed throughout the study per the Lab Processing Chart (LPC). Collection of sample aliquots is of particular importance at the pre-sirolimus time points (entry and week 12) and at the study week 32 time point. In the event that the required volume or number of sample aliquots is not obtained at any time point, designated site clinic and/or lab staff must immediately inform the study team, who will provide guidance on how to respond to the problem.

In addition to following this guidance from the study team, designated site clinic and lab staff will work together to document the problem, take appropriate corrective and preventive action, and document all action taken. Reconciliation must be performed for all specimen types that are received by the laboratory and stored in the LDMS.

For other evaluations, if an evaluation is not completed at a scheduled visit, effort should be made to obtain the evaluation as soon as possible. If unsuccessful, complete the evaluation at the next study visit if not already included as part of the regularly scheduled visit.

NOTE: Sites must contact the A5337 core team prior to the scheduled week 12 visit, ideally at least 2 weeks before, for confirmation that a **participant** may begin study treatment based on availability of stored samples at study entry. This confirmation must be documented in the source document prior to initiation of sirolimus.

On-Treatment Evaluations (weeks 12 through 32)

The window for week 12 is ± 1 week and for weeks 13 through 16 is ± 1 day as visits will be timed with the PK evaluations. The window for weeks 20 through 32 is ± 1 week.

NOTE: Starting with week 12, days should be counted from the first date of actual sirolimus dosing. Day 0 is the date of the first dose of sirolimus.

Post-Treatment Evaluations (week 44)

The week 44 visit is the final study visit. The window for the week 44 visit is ± 2 weeks.

Event Driven Evaluations

Confirmation visit to confirm CD4+ cell count <300 cells/mm 3 or $>50\%$ CD4+ decrease from study entry value or HIV-1 RNA >200 copies/mL (see sections 7.1.4 and 7.1.5) should be scheduled within 1 week of receipt of the abnormal lab value. If confirmed CD4+ cell count <300 cells/mm 3 or $>50\%$ CD4+ decrease from study entry value or HIV-1 RNA >200 copies/mL, the study team should be promptly contacted and sirolimus should not be started or should be stopped if already started.

6.2.4 Discontinuation Evaluations

Evaluations for Registered Participants Who Do Not Start Study Treatment

Site personnel should notify the protocol team ([contact]) within 48 hours of any **participant** who is registered and does not begin treatment at week 12. All case report forms must be completed and keyed for the period up to and including week 12. **Participants** who do not start study treatment at week 12 will be taken off the study and will be replaced after completing all week 12 evaluations listed on the SOE.

Premature Treatment Discontinuation Evaluations

Participants who prematurely discontinue the study treatment prior to week 32 will have the Premature Treatment Discontinuation visit per the SOE, performed as soon as possible, and then continue study follow-up through week 44. **Participants** should have all PK sampling performed until the next scheduled dosing visit; then PK sampling should be discontinued. **Participants** will be followed on study/off study treatment.

Site personnel should notify the protocol core team ([contact]) within 48 hours of any **participant** who prematurely discontinues the study treatment.

Premature Study Discontinuation Evaluations

Participants who prematurely discontinue the study will have the Premature Study Discontinuation visit per the SOE, performed as soon as possible prior to being taken off the study.

Site personnel should notify the protocol core team ([contact]) within 48 hours of any **participant** who prematurely discontinues the study.

6.3 Instructions for Evaluations

All clinical and laboratory information required by this protocol is to be present in the source documents. Sites must refer to the Source Document Guidelines on the DAIDS Web site for information about what must be included in the source document:

<http://www.niaid.nih.gov/labsandresources/resources/daidsclinsrch/documents/sourcedocappndx.pdf>

All stated evaluations are to be recorded on the CRF and keyed into the database unless otherwise specified. This includes events that meet the International Council on Harmonisation (ICH) definitions for a serious adverse event:

- Results in death
- Life-threatening
- Requires inpatient hospitalization or prolongation of existing hospitalization
- Results in persistent or significant disability/incapacity
- Congenital anomaly/birth defect
- Other important medical event (may not be immediately life-threatening or result in death or hospitalization but may jeopardize the patient or may require intervention to prevent one of the events listed above).

To grade diagnoses, signs and symptoms, and laboratory results, sites must refer to the DAIDS Table for Grading the Severity of Adult and Pediatric Adverse Events (DAIDS AE Grading Table), **Version 2.0, November 2014** which can be found on the DAIDS RSC Web site: <http://rsc.tech-res.com/safetyandpharmacovigilance/>.

6.3.1 Documentation of HIV-1

Section 4.1.1 specifies assay requirements for HIV-1 documentation. HIV-1 documentation is not recorded on the CRF.

6.3.2 Medical History

The medical history must include all diagnoses within the 30 days prior to study entry identified by the ACTG criteria for clinical events and other diagnoses, as well as the following diagnoses, regardless of when the diagnosis was made, and recorded on a CRF. For current criteria, refer to the appendix identified on the study CRF.

- AIDS-defining conditions
- Bone fractures (verbal history accepted)
- Coronary heart disease
- Cancer
- Myelodysplastic, myeloproliferative or lymphoproliferative disorders
- Diabetes
- Tuberculosis
- Non-tuberculous mycobacterial infection
- Chronic hepatitis B
- Chronic hepatitis C
- Human papilloma virus (HPV; including cervical dysplasia/neoplasia and anogenital warts)
- Kidney disease
- Obstructive or restrictive lung disease
- Interstitial lung disease
- Endocrine disorders including fertility disorders
- Thyroid disease
- Treatment for HPV-related disease

Any allergies to any medications and their formulations must also be documented. **Document the pre-ART HIV-1 RNA level and CD4+ count, if available. If pre-ART HIV-1 RNA level or CD4+ count documentation is not available, then collect and record what the participant remembers. Document the date of first undetectable HIV-1 RNA level prior to sustained viral load suppression (may be estimated if exact date not available) and the date(s) of any previous virologic failure on ART. The medical history evaluation will be assessed at the screening and entry visit and recorded on the CRFs at the study entry visit.**

6.3.3 Medication History

A medication history must be present, including start and stop dates. The table below lists the medications that must be included in the history.

Medication Category	Timeframe
Antiretroviral therapy	Complete history (start and stop dates required only for ART taken within past 2 years and date of first use of ART)
Immune-based therapy (e.g., interleukins, interferons, cyclosporine, TNF-modulating drugs/monoclonal antibodies)	Complete history
HIV-1-related vaccines	Complete history
Drugs for treatment or prevention of opportunistic infections	Complete history
Prescription and non-prescription drugs	All cardiac or renal medications taken currently and within 12 months prior to study entry (including HMG-CoA reductase inhibitors, calcium channel blockers) All other medications within 3 months prior to study entry
Dietary supplements	Within 3 months prior to study entry
Any prohibited medications. See section 5.4.2.	30 days prior to study entry

6.3.4 Clinical Assessments

Complete Physical Exam

A complete physical examination to include at a minimum an examination of the skin, head, mouth, and neck; auscultation of the chest; cardiac exam; abdominal exam; examination of the lower extremities for edema. The complete physical exam will also include signs and symptoms, diagnoses and vital signs (temperature, pulse, respiration rate, pulse oximetry and blood pressure).

Targeted Physical Exam

A targeted physical examination to include vital signs (temperature, pulse, respiration rate, pulse oximetry and blood pressure); examination of the skin, head, mouth, and neck; auscultation of the chest; cardiac exam; and is to be driven by any previously identified or new signs or symptoms and diagnoses that the **participant** has experienced since the last visit. Assessment of new pulmonary symptoms, including cough, shortness of breath and dyspnea on exertion will be included in the targeted exam.

Height

Height will be recorded at entry.

Weight

Weight will be recorded at entry and **all subsequent study visits**.

Signs and Symptoms

At entry, all grades of signs and symptoms that occurred within 30 days before entry must be recorded; post-entry, all grades of Grade ≥ 2 must be recorded. Record **on the CRF and key within 48 hours** all signs and symptoms regardless of grade that led to a change in study treatment or a change in ART. All Grade 3 or higher sign/symptom, any sign/symptom regardless of grade that led to a change in study treatment, or that met ICH, EAE or SAE guidelines, are defined by the protocol as reportable events that will require more detailed event reporting and keying within 48 hours.

Diagnoses

After entry, record all diagnoses identified by the ACTG criteria for clinical events and other diseases. Diagnoses must be recorded and keyed within 48 hours of the evaluation.

Concomitant Medications

After entry, record new or discontinued concomitant prescription and nonprescription drugs since the last visit.

ART Medication Modifications

At entry, record all ongoing ART. After entry, record all modifications in ART, including initial doses and/or missed doses (defined as more than 2 consecutive doses), inadvertent and deliberate interruption, and discontinuation.

Study Treatment Modifications

Record **on the CRF and key within 48 hours** all modifications in sirolimus dosing, including initial doses and/or missed doses, inadvertent and deliberate interruption and **permanent** discontinuation.

6.3.5 Laboratory Evaluations

Refer to the A5337 Laboratory Processing Chart (LPC) posted on the PSWP for processing, shipping, and storage information.

The screening and entry protocol-required laboratory values, regardless of grade, must be recorded. For post-entry assessments, record **on the CRF and key within 48 hours**, lipid values, glucose, hematology, liver function tests, calculated CrCl, serum creatinine values regardless of grade and all other Grade ≥ 3 laboratory values. In addition, record **on the CRF and key within 48 hours** all laboratory values regardless of grade that led to a change in study treatment or a change in ART. All Grade 3 or higher laboratory values, any laboratory value regardless of

grade that led to a change in study treatment, or that met ICH, EAE or SAE guidelines, are defined by the protocol as reportable events that will require more detailed event reporting and keying within 48 hours.

Hematology

Hemoglobin, hematocrit, white blood cell count (WBC) with differential, absolute neutrophil count (ANC), platelets.

Liver Function Tests

Total bilirubin, direct bilirubin, indirect bilirubin, albumin, AST (SGOT), ALT (SGPT), alkaline phosphatase, creatine kinase (CK).

Blood Chemistries

Glucose, triglycerides, cholesterol (total, LDL), electrolytes (e.g., sodium, potassium, chloride, bicarbonate), lactate dehydrogenase (LDH), creatinine, blood urea nitrogen (BUN), total protein, albumin, globulin (globulin may need to be calculated from the total protein and albumin). Lipid levels may be drawn non-fasting (see section 7.2.5 for management of elevated levels).

Calculated CrCl

Estimated each time that a serum creatinine level is determined. To estimate calculated CrCl, use the Cockcroft and Gault equation (see section 4.1.10).

Urinalysis

Random urinalysis for urine protein to urine creatinine ratio.

Pregnancy Test

For women with reproductive potential: At screening (before chest x-ray) negative serum or urine pregnancy test with a sensitivity range of ≤ 25 mIU/mL, 48 hours prior to study entry and again at week 12 with results available before initiation of study drug, and at any time during the study when pregnancy is suspected.

Hepatitis Serology

For **participants** with known HBV immunity, prior documentation of positive HBsAb is acceptable. If documentation is not available, HBsAb, HBsAg, and HBcAb will be obtained at screening. Negative HBV tests (i.e., negative HBsAb, HBsAg, and HBcAb) performed within 6 months prior to enrollment need not be repeated. If the last negative test result is more than 6 months prior to enrollment, then testing should be performed at screening. Results must be available prior to study entry so that **participants** who have active HBV can be excluded from participating in the study.

Participants who have positive HBcAb but negative HBsAg and HBsAb (isolated HBcAb positive status) must have HBV DNA PCR performed and confirmed as negative for **participant** to be eligible for A5337. HBV DNA PCR will not be provided by A5337.

HCV antibody test (and HCV RNA if the HCV Ab test is positive) should be obtained at screening. Results must be available prior to study entry.

Assessment for Reactivation Latent EBV

Performed on serum or plasma using a clinical quantitative PCR-based test at a laboratory that has CLIA certification or its equivalent (see section 7.1.6) and results from all testing recorded on a CRF.

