4.0 SELECTION AND ENROLLMENT OF PARTICIPANTS

4.1 Inclusion Criteria

- 4.1.1 HIV-1 infection, documented by any licensed rapid HIV test or HIV enzyme or chemiluminescence immunoassay (E/CIA) test kit at any time prior to study entry and confirmed by a licensed Western blot or a second antibody test by a method other than the initial rapid HIV and/or E/CIA, or by HIV-1 antigen, plasma HIV-1 RNA viral load.

WHO (World Health Organization) and CDC (Centers for Disease Control and Prevention) guidelines mandate that confirmation of the initial test result must use a test that is different from the one used for the initial assessment. A reactive initial rapid test should be confirmed by either another type of rapid assay or an E/CIA that is based on a different antigen preparation and/or different test principle (e.g., indirect versus competitive), or a Western blot or a plasma HIV-1 RNA viral load.

- 4.1.2 Currently on continuous ART for ≥ 24 months prior to study entry. This is defined as continuous active therapy for the 24-month period prior to study entry with no treatment interruption longer than 7 consecutive days.

- 4.1.3 CD4+ cell count ≥ 350 cells/mm 3 obtained within 60 days prior to study entry at any US laboratory that has a CLIA certification or its equivalent, or at any

network-approved non-US laboratory that operates in accordance with Good Clinical Laboratory Practices (GCLP) and participates in appropriate external quality assurance programs.

- 4.1.4 Plasma HIV-1 RNA below the level of quantification (e.g., <20, <40, <50, or <75 copies/mL depending on the assay) for ≥ 24 months by an FDA-approved assay at any US laboratory that has a CLIA certification or its equivalent, or at any network-approved non-US laboratory that operates in accordance with GCLP and participates in appropriate external quality assurance programs. Participants must have at least one documented HIV-1 RNA below the level of quantification obtained 12-24 months prior to screening **HIV-1 RNA** and one HIV-1 RNA less than the level of quantification obtained within 12 months prior to the screening **HIV-1 RNA by an FDA-approved assay** (see section 4.1.5)

NOTE: One month = 30 days.

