 - Aspartate aminotransferase (AST) $< 1.25 \times \text{ULN}$
 - Alanine aminotransferase (ALT) $< 1.25 \times \text{ULN}$
 - Calculated creatinine clearance (CrCl) $\geq 60 \text{ mL/min}$ as estimated by the Cockcroft-Gault equation:
For men, $(140 - \text{age in years}) \times (\text{body weight in kg}) \div (\text{serum creatinine in mg/dL} \times 72) = \text{CrCl (mL/min)}^*$
*For women, multiply the result by 0.85 = CrCl (mL/min)
- NOTE:** A program to assist in calculations is available on the DMC website at: <http://www.fstrf.org/ACTG/ccc.html>
- Fasting or non-fasting triglyceride level $\leq 350 \text{ mg/dL}$
 - Fasting or non-fasting LDL $< 160 \text{ mg/dL}$
 - Urine protein to urine creatinine ratio $\leq 1 \text{ g/g}$ from random urine collection

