4.2 Exclusion Criteria

- 4.2.1 Serious illness requiring systemic treatment and/or hospitalization until **participant** either completes therapy or is clinically stable on therapy in the opinion of the site investigator for at least 30 days prior to study entry.
- 4.2.2 Documentation of any CDC Category C AIDS-indicator condition or oropharyngeal candidiasis (thrush) within 90 days prior to study entry. (<http://www.cdc.gov/mmwr/preview/mmwrhtml/00018871.htm>)
- 4.2.3 Intended modification of ART during the study.

- 4.2.4 Latent tuberculosis (TB) infection defined as a positive purified protein derivative (PPD) ≥ 5 mm or positive interferon-gamma release assay (IGRA) at any time in the past or evidence of latent TB on the screening chest x-ray without subsequent isoniazid or equivalent antibiotic prophylaxis.

NOTE: Prophylaxis must have been completed at least 48 weeks prior to study entry.

- 4.2.5 TB disease within 48 weeks prior to study entry requiring treatment. **Participants** with a history of active TB must have completed treatment at least 48 weeks prior to study entry.

- 4.2.6 History of or current (within 90 days prior to study entry) active hepatitis B (HBV) infection defined as positive HBV surface antigen test or positive HBV DNA in **participants** with isolated HBcAb positivity.

- 4.2.7 HCV RNA-positive within 90 days prior to study entry.

NOTE: **Participants** who are HCV antibody negative within 90 days prior to study entry are eligible for the study. Those who are not taking HCV therapy and who are HCV antibody-positive but HCV RNA negative within 90 days prior to study entry are eligible for the study.

- 4.2.8 Previously diagnosed myelodysplasia syndrome.

- 4.2.9 History of lymphoproliferative disease prior to study entry.

- 4.2.10 Clinically significant lung disease on the screening chest x-ray that, in the opinion of the site investigator, places the **participant** at increased risk of lung toxicity (e.g., history of pulmonary fibrosis, interstitial lung disease or pulmonary lymphoproliferative disease).

- 4.2.11 Any prior or current diagnosis of solid tumor or hematologic malignancies, **excluding a history of fully excised or resolved non-melanoma skin cancers without evidence of prior or current metastasis.**

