6.0 CLINICAL AND LABORATORY EVALUATIONS

6.1 Schedule of Events

Evaluation	Screening	Entry	Sirolimus Initiation	Post-Entry Evaluations								Premature Treatment or Study Discontinuation	Confirmation of CD4 Decrease	Confirmation of Virologic Failure
	Week	0	12	13	14	16	20	24	32	44				
Days Post-Sirolimus Initiation			0	4	11	28	56	84	140	224				
Window	Within 60 days prior to entry		±1 week	±1 day (same days as PK)			±1 week (same days as PK)			±2 weeks				
Documentation of HIV	X													
Medical & Medication History	X	X												
Clinical Assessment	X	X	X	X	X	X	X	X	X	X	X			
Complete Physical Exam	X													
Targeted Physical Exam		X	X		X	X	X	X	X		X	X	X	
Hematology	X	X	X	X	X	X	X	X	X	X	X			
Liver Function Tests	X	X	X	X	X	X	X	X	X	X	X			
Blood Chemistry	X	X	X	X	X	X	X	X	X	X	X			
Calculated Creatinine Clearance	X	X	X	X	X	X	X	X	X	X	X			
Urinalysis	X		X		X	X	X							
Pregnancy Testing	X	X	X	if indicated										
Hepatitis Serology (see section 6.3.5)	X													
Assessment for Reactivation of Latent EBV	X						X	X	X	X	X			
CD4+/CD8+	X	X	X	X	X	X	X	X	X	X	X			

Evaluation	Screening	Entry	Sirolimus Initiation	Post-Entry Evaluations								Premature Treatment or Study Discontinuation	Confirmation of CD4 Decrease	Confirmation of Virologic Failure	
	Week	0	12	13	14	16	20	24	32	44					
Days Post-Sirolimus Initiation			0	4	11	28	56	84	140	224					
Window	Within 60 days prior to entry			±1 week	±1 day (same days as PK)			±1 week (same days as PK)			±2 weeks				
Cryopreserved PBMCs for HIV-1 Gag-specific CD8+ and CD4+ cell Immunity		X	X	X		X		X	X	X		X			
Stored Plasma for Inflammatory and Coagulation Markers		X	X	X		X		X	X	X		X			
Cryopreserved PBMCs for Markers of T-cell Activation and Proliferation		X	X	X		X		X	X	X		X			
Cryopreserved PBMCs for Exploratory Studies		X	X	X		X	X	X	X	X		X			
Stored Plasma for Antibody Quantitation		X	X	X				X	X	X		X			
Plasma HIV-1 RNA	X	X	X			X	X	X	X	X		X			X
HIV-1 Drug Resistance Genotyping (see section 6.3.7)															X
Cryopreserved PBMCs for Inducible RNA Assay			X					X	X	X					
Cryopreserved PBMCs for Cell-Associated RNA and DNA		X	X	X		X		X	X	X		X			
Stored Plasma for Residual Viremia by Single-Copy RNA Assay		X	X	X		X		X	X	X		X			
Stored Whole Blood for Gene Expression Assay			X	X		X		X	X	X					
Stored Plasma and PBMCs for Future Unspecified Testing		X	X	X		X		X	X	X		X			
Tuberculosis Test (see section 6.3.11)	X														
Chest Radiograph	X														
Anal Swabs/Anal Pap Test			X						X						

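### Hepatitis B serology up to 6 months old is accepted for non-immune participants, although the exclusion counts infection as current within 90 days of entry

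*Protocol*

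**What the plan says.** Section 4.2.6 of the protocol excludes "History of or current (within 90 days prior to study entry) active hepatitis B (HBV) infection defined as positive HBV surface antigen test". For someone whose only positive marker is HBcAb, a positive viral DNA result counts as well.

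Section 6.3.5 (Hepatitis Serology) sets the testing. Documented HBsAb positivity is accepted as evidence of immunity. Without such documentation, all three markers are drawn at screening. For people already found negative on all three, the rule is "Negative HBV tests (i.e., negative HBsAb, HBsAg, and HBcAb) performed within 6 months prior to enrollment need not be repeated", followed by "If the last negative test result is more than 6 months prior to enrollment, then testing should be performed at screening". The same section gives the purpose: results are needed before entry so that active hepatitis B can be excluded.

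For hepatitis C, the note to section 4.2.7 puts the age of the negative result in the criterion itself: participants "who are HCV antibody negative within 90 days prior to study entry are eligible for the study".

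**The concern.** Section 6.3.5 is the procedure that puts section 4.2.6 into effect, but the two use different time limits. The longer limit applies to people negative for HBsAb, who have no immunity and can still be infected. For such a person with a panel 91 to 180 days old, the site holds no hepatitis B result from the period in which the exclusion counts infection as current. Someone infected after that panel could be enrolled and then start sirolimus, whose boxed warning (section 2.1.5) includes increased susceptibility to infection. At stake is consistent eligibility screening and a small safety margin. The efficacy and safety analyses are not involved.

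**Working it through.** The plan states no figure to reproduce. The check compares the two time limits and then asks whether any other rule closes the gap.

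**Inputs**
- Window for current hepatitis B: 90 days before study entry (4.2.6).
- Maximum age of an accepted triple-negative panel: 6 months before enrollment (6.3.5). I take enrollment and study entry as the same day.
- Month length: "One month = 30 days" (note to 4.1.4). That note sits under another criterion; I assume it applies here too.
- Nominal first sirolimus dose: week 12, which is 12 x 7 = 84 days after entry.

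**Test age at entry**
- Maximum accepted age: 6 x 30 = 180 days.
- Excess over the exclusion window: 180 - 90 = 90 days, that is, panels aged 91 to 180 days.
- With calendar months (181 to 184 days), the excess is 91 to 94 days.
- With a 90-day rule, the excess is 0 and the maximum age falls to 90/180 = 50% of the present limit.

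**Test age at nominal first dose**
- Now: 180 + 84 = 264 days.
- With a 90-day rule: 90 + 84 = 174 days, a reduction of 90/264 = 34%.
- The 84 days of lead-in apply to every test done only at screening and are not part of the mismatch.

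**Who falls in the gap**

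| Participant | Rule in 6.3.5 | Hepatitis B result within 90 days of entry? |
|---|---|---|
| Documented HBsAb positive | No new test | Not needed; immune |
| No documentation | Tested at screening | Yes |
| Triple negative, 0 to 90 days old | No repeat | Yes |
| Triple negative, 91 to 180 days old | No repeat | **No** |
| Triple negative, over 6 months old | Tested at screening | Yes |

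The two screening rows rely on the 60-day screening window in section 6.2.1.

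**Does another rule supply a result?**
- HBV DNA is required only for isolated HBcAb positivity, so it never reaches a triple-negative participant.
- The 60-day window in 6.2.1 gives way where the protocol specifies otherwise, and 6.3.5 does. That settles which rule a site follows; it does not bring 6.3.5 into line with 4.2.6.
- The Schedule of Events (6.1) lists hepatitis serology at screening only and refers back to 6.3.5.
- Before sirolimus, section 6.2.3 says the week-12 laboratory results "must be assessed to ensure that the criteria detailed in section 4.1.6 and 4.1.10 continue to be satisfied". Section 4.1.10 includes AST and ALT below 1.25 x ULN, which may flag some acute infections. No hepatitis B test is repeated.

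No rule closes the gap before the first dose.

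**The case against.** The strongest reply is that the sections do not contradict each other. The 90 days in 4.2.6 qualifies current infection and does not say how recent a negative test must be. Because any history is also excluded, a positive result 120 days before entry excludes as surely as one at 60 days. Section 6.3.5 is explicit, the Schedule of Events points to it, and a site has one clear instruction. The different hepatitis C rule could be deliberate. Also, any screening test misses later infection: at first dose the oldest panel would still be about 174 days old after the change. Liver tests continue at entry and at every on-treatment clinical visit, and section 7.2.1 stops sirolimus if ALT or AST exceeds 5 x ULN. Harm would need a triple-negative participant, a panel 91 to 180 days old, a new infection since then, and enzymes still within limits at screening and week 12.

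Much of this stands. It is a mismatch, not a literal contradiction; the gain at first dose is 34%, not 50%; and enzyme monitoring is a real, though non-specific, safeguard that continues on treatment. What remains is that a panel 91 to 180 days old cannot show whether someone had hepatitis B in the period the exclusion names, and the protocol gives no reason for allowing an older negative result for hepatitis B than for hepatitis C.

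**Conclusion.** The concern holds, as a minor one. For triple-negative participants with a panel 91 to 180 days old, section 6.3.5 does not deliver the check that section 4.2.6 implies. The excess test age at entry is at most 90 days, or 91 to 94 with calendar months. This assumes that the 30-day month carries over from 4.1.4 and that enrollment and study entry fall on the same day. The documents give neither the incidence of hepatitis B nor the share of participants who would be triple negative, so an expected number affected cannot be calculated; among 30 participants it is likely very small. No primary outcome, sample size or analysis depends on it.

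**What to change.** In section 6.3.5, replace the 6-month limit before enrollment with 90 days before study entry, both in the sentence that waives repeat testing and in the one that triggers it. Leave section 4.2.6 unchanged. Older triple-negative results would then be repeated at the screening draw, matching the 90-day hepatitis C rule in 4.2.7.

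The cost is one clarification memo, plus repeat HBsAb, HBsAg and HBcAb for the few triple-negative participants whose last panel is 91 to 180 days old. No extra visit is needed, because hepatitis serology is already scheduled at screening.
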